# SCHEDULE OF ASSESSMENTS

Period	Screening a, b	Study Drug Treatment Period c									In-hospital Post-Treatment Period d	FU visit (Day 14±2) or Withdrawal visit e	EOS e (Day 28±2)			
		Hospitalized Dosing						Hospitalized or Ambulatory Dosing								
		Day 1			Day 2			Day 3								
Visit	-24h to randomization	-3h to dose	Dose	2h (±0.5h)	5h (±1h)	-2h to dose	Dose	2h (±0.5h)	5h (±1h)	-2h to dose	Dose	2h (±0.5h)	Morning and evening			
Informed consent	X															
Inclusion/exclusion criteria	X															
RSV diagnosis f	X															
Demographics and medical history	X															
Hospitalization information/Clinical response information g																→
Study drug administration h			X				X				X					
Nasal mid-turbinate swab i		X			X	X			X	X		X	X j	X		
Physical examination k	X	X			X	X			X	X		X	X	X	X	X
Body weight	X														X	X
Body height	X														X	X
Body temperature	X	X			X	X			X	X		X	X	X	X	X
General appearance	X	X			X	X			X	X		X	X	X	X	X
Lung auscultation n	X	X		X	X	X		X	X	X		X	X	X	X	X
Heart rate	X	X		X	X	X		X	X	X		X	X	X	X	X
SpO 2 l	X	X		X	X	X		X	X	X		X	X	X	X	X
Feeding m	X	X			X	X			X	X		X	X	X	X	X
(Respiratory muscle) retractions	X	X		X	X	X		X	X	X		X	X	X	X	X
Respiratory rate	X	X		X	X	X		X	X	X		X	X	X	X	X
Randomization b		X														
Daytime coughing	X	X		X	X	X		X	X	X		X	X	X	X	X
(Sleep disturbance from) night-time coughing o	X o	X o				X o				X o			X o	X o	X o	X
Parent/caregiver assessment p																→
Pharmacokinetics (single sample)																← → q
Pharmacokinetics (more extensive sampling)						X r										← → r ← → r
Clinical laboratory (hematology and clinical biochemistry)	X s, t														X u	
Immunogenicity	X s														X u	
Previous and concomitant medication																→
Adverse events v																→

h = hour; FU = Follow-up; EOS = End of Study.

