- e. For subjects who discontinue the study before Day 28, the Withdrawal visit will be conducted on the day of withdrawal as long as there has been no withdrawal of consent. If the Withdrawal visit assessments are performed within 6 hours after the Day 1, Day 2, Day 3, or in-hospital post-treatment Day assessments have been performed, the assessments already done at the prior time point do not need to be repeated and only the additional assessments to be performed on the Withdrawal Visit will need to be performed. No EOS visit needs to be performed after the Withdrawal Visit. In case subjects are hospitalized beyond the Day 14 FU visit, the additional assessments (in addition to the in-hospital post treatment period assessments) of the Day 14 FU visit need to be done on Day 14.
- f. RSV infection will be confirmed either according to routine site practice (PCR or diagnostic quick test), or using a (Sponsor-provided) commercial kit.
- g. Hospitalization information will include occurrence of ICU transfer, apnea episodes, initiation and type of ventilation and hospital/ICU discharge information. Assessment of Clinical Response will be done with collection of date and time of adequate oral feeding to enable discharge as well as adequate stable oxygen saturation on room air of  $>92\%$  over a period of at least 4 hours.
- h. Study drug will be administered via nebulization using the study-specific device. One dose consists of 2 serial nebulizations.
- i. A mid-turbinal nasal swab should be taken using provided kits and following specific instructions in case the subject is re-hospitalized or consults the Investigator for a respiratory condition after hospital discharge.
- j. A nasal swab should only be collected during the in-hospital post-treatment period on the day of hospital discharge.
- k. Physical examination includes examination of abdomen and skin and ears/nose/throat. Lung auscultation is listed separately as it is to be assessed more frequently.
- l. Continuous monitoring of SpO2 needs to be done until the clinical response criterion for oxygen has been met and/or in case saturation monitoring is to be continued according to the Investigator's judgment.
- m. Type of feeding support, if any, and feasibility of oral feeding.
- n. To assess wheezing, crackles/crepitation and other abnormalities in lung auscultation.

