- o. Sleep disturbance from night-time coughing to be documented pre-dose the next day or in the morning during the in-hospital post-treatment period, or at the FU visit, EOS or Withdrawal visit, based on feedback from the nursing staff. In case there is no night between screening and study drug administration on Day 1, the Day 1 assessment should not be performed.
- p. The parent/caregiver assessment should be done every evening from screening until the EOS visit by completing a diary.
- q. Blood draw for PK assessments on Day 2 or Day 3, at any time between 0.5 hours post second dose and start of the third dose. If sufficient serum remains after PK assessment, exploratory biomarker (KL-6) may also be evaluated.

- 
- r 48 subjects will undergo more extensive PK analysis (3 PK samples per subject instead of the 1 sample), i.e., blood draws on Days 2-3 1) pre second dose, 2) at any time between 0.5 hours and 3 hours post second dose, and 3) at any time between 3 hours and 6 hours post second dose (and at least 1 hour apart from the previous sampling); If sufficient serum remains after PK assessment, exploratory biomarker (KL-6) may also be evaluated.
- s Blood draw at screening for clinical laboratory (hematology and clinical biochemistry) and immunogenicity. If sufficient serum remains after immunogenicity assessment, exploratory biomarker (KL-6) may also be evaluated. In case the blood sample for immunogenicity was not taken at screening, the sample should be collected at the Day 1 pre-dose timepoint, as far as possible.
- t If all hematology and biochemistry blood parameters required for the study are already known from analysis done as a routine assessment upon arrival at the hospital, collection of screening clinical laboratory samples does not need to be repeated for the purpose of this study. However, the samples should be analyzed at the same local laboratory that will be used for the remainder of the study.
- u Blood draw on Day 14 for clinical laboratory (hematology and clinical biochemistry) and immunogenicity. If sufficient serum remains after immunogenicity assessment, exploratory biomarker (KL-6) may also be evaluated. No blood sample needs to be taken in case of premature withdrawal from the study for subjects who did not receive any study drug. In case the blood sample for immunogenicity was not taken on Day 14, the sample should be collected at the EOS (Day 28) visit, as far as possible.

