## Immunogenicity

- In adults, pre-existing antibodies (pre-Ab§) were found in 7 to 18% of the subjects. In the Phase 1 studies ALX-0171-1.1/11 and ALX-0171-1.3/13, no treatment-emergent (TE) ADA responses were detected, whereas in the Phase 1 safety study ALX-0171-1.2/13, TE ADA were observed in 33% of the subjects (population of subjects with hyperresponsive airways).
- In Study ALX-0171-C104, pre-Ab were found in 45% of the subjects, while TE ADA was detected in 22.9% of the infants. Pre-Ab detected in those children may reflect maternal antibodies transferred to the infant via the transplacental route during gestation or during breastfeeding. As the assay cannot discriminate pre-Ab from drug induced TE ADA, it is not clear to what extent the TE ADA detected may represent fluctuating levels of pre-Ab. Currently it is not known to what extent pre-Ab can fluctuate within the short study period (14 days). No effect of ADA on PK was observed.

TE ADA is not expected to have an impact on PK or efficacy given the short treatment duration, as TE ADA do not emerge to considerable amounts within the first 7 days after initial drug administration.

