### 3.2.3. REMOVAL OF SUBJECTS FROM THERAPY OR ASSESSMENT

Every reasonable attempt should be made by the Investigator (or his/her designee) to keep subjects in the study, however, a subject must be withdrawn from the study if:

- Study drug administration cannot be successfully initiated on Day 1 (see section 3.3.7.2).
- The Investigator considers it, for safety reasons, in the best interest of the subject.
- The parent(s)/legal guardian(s) withdraw(s) consent.

A subject may be withdrawn from the study if the subject and/or parent(s)/legal guardian(s) fail to comply with dosing, evaluations, or other requirements of the study.

Investigators (or their designees) must attempt to contact the parent(s) or legal guardian(s) of subjects who fail to attend scheduled visits by telephone or other means, to exclude the possibility of an AE being the cause of withdrawal. Should this be the cause, the AE must be documented, reported, and followed-up as described in section 3.5.

If a subject is prematurely withdrawn from the study, the reason for withdrawal and the date of withdrawal will be recorded in the eCRF. Whenever possible and reasonable, a Withdrawal visit should be conducted at the time of withdrawal (no EOS visit).

A subject must be discontinued from study drug treatment if:

- The randomization code is broken prematurely by the Investigator or Sub-Investigator.
- A severe and/or serious hypersensitivity reaction occurs
- A severe and/or serious acute respiratory distress reaction induced by study drug administration occurs
- The subject needs to start treatment with one of the medications listed as prohibited (see section [3.3.8](#))
- The subject needs to start non-invasive respiratory support, invasive ventilation or HFOT at levels not enabling removal of the cannula for administration of the study drug nebulization and/or levels exceeding 2 L/kg/min. The event will be captured as an SAE and will be monitored until resolution, as described in section [3.5](#).
- If the investigator or the Sponsor / medical monitor deems it is in the subject's best interest

A subject may be discontinued from study drug treatment if an SAE occurs (if considered necessary or appropriate by the Investigator).

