### 11.1 Available data

#### 11.1.1 ADA

Immunogenicity of ALX-0171 was monitored in all clinical studies using MSD-based homogeneous bridging ADA assays via a tiered approach. In a first step, samples are evaluated in a screening assay and are scored possibly ADA positive based on the screening

cut-point (SCP), allowing a 5% false positivity rate. Positively screened samples are subsequently analyzed in a confirmation assay, which is a drug displacement assay to confirm the specificity of the ADA screening result. All positively confirmed samples are subsequently analyzed in an end-point titration assay to determine the antibody titer. The  $\log_{10}(\text{titer})$  will be reported. The titer represents the last dilution factor of the sample's titration series still scoring positive in the ADA assay. Samples scoring negative in the ADA assay are not titrated and the respective  $\log_{10}(\text{titer})$  is reported as  $<\log_{10}(\text{Minimal required dilution [MRD]})$  with  $\text{MRD}=24$ , i.e.  $\log_{10}(\text{titer}) < 1.38$ . The latter negative samples are not included in descriptive statistics on titers.

For each subject, immunogenicity results will be categorised based on the presence of pre-existing antibodies (pre-Ab) and the presence of treatment-emergent (TE) ADA, as shown below. Classification is performed by the Bioanalytical laboratory (Ablynx GLP-Pharma) performing the ADA sample analysis and they report both  $\log_{10}(\text{titer})$  and subject classification.

Subjects will be classified based on the pre-Ab and TE ADA status (subject classifications):

1. Pre-Ab NEG – TE ADA NEG
2. Pre-Ab NEG – TE ADA POS
3. Pre-Ab POS – TE ADA NEG
4. Pre-Ab POS – TE ADA POS
5. Pre-Ab POS – TE ADA EQ
6. TE ADA inconclusive: Pre-Ab NEG – Post-dose missing
7. TE ADA inconclusive: Pre-Ab POS – Post-dose missing
8. TE ADA inconclusive: Pre-dose missing – Post-dose NEG
9. TE ADA inconclusive: Pre-dose missing – Post-dose POS

Note: Subject classification 'Inconclusive TE ADA' (that is generally used in case drug tolerance is exceeded) is not included here since drug washout samples are available for ADA testing.

Below subject categories are only to be used in the tables and figures on incidence and subgroup analysis (for all other figures and tables subject classifications are used as described above).

Possible subject categories:

1. Pre-Ab NEG – TE ADA NEG
2. Pre-Ab NEG – TE ADA POS
3. Pre-Ab POS – TE ADA NEG
4. Pre-Ab POS – TE ADA POS

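### SAP 11.1.1 has no class for an anti-drug-antibody sample taken too early, so a negative sample from a dosed infant withdrawn in the first week falls by default into TE ADA negative

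*SAP*

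**What the plan says.** **Sampling.** In the protocol's Schedule of Assessments, the post-dose immunogenicity sample sits in the column headed "FU visit (Day 14±2) or Withdrawal visit". Footnote e states that "the Withdrawal visit will be conducted on the day of withdrawal as long as there has been no withdrawal of consent", and later "No EOS visit needs to be performed after the Withdrawal Visit". Footnote u waives the draw for one group only: "No blood sample needs to be taken in case of premature withdrawal from the study for subjects who did not receive any study drug". Protocol 3.4.1.3 requires a Withdrawal visit except after loss to follow-up or consent withdrawal.

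**Classification.** SAP 11.1.1 lists nine subject classes. Classes 6 to 9 are inconclusive, and each is defined by an absent pre-dose or post-dose sample. No class depends on when the sample was taken. The further class normally kept for exceeded drug tolerance "is not included here since drug washout samples are available for ADA testing". SAP 11.1.2 adds that infants with no ADA-positive sample are not run in the neutralizing-antibody (NAb) assay and go into NAb class 1, negative before dosing and negative on treatment.

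**Time course.** Protocol 1.2.3 says that "TE ADA do not emerge to considerable amounts within the first 7 days after initial drug administration". Protocol 1.3.3 repeats this and expects drug to be cleared by the time such antibodies would appear.

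**Withdrawal rules.** Protocol 3.2.3 gives, as a reason that requires withdrawal from the study, "The Investigator considers it, for safety reasons, in the best interest of the subject". As a reason that requires stopping study drug, it gives "If the investigator or the Sponsor / medical monitor deems it is in the subject's best interest".

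**The concern.** A negative result is informative about TE ADA only if antibodies had time to form and drug in the sample did not mask them. A Withdrawal sample from the first days may fail on both counts, yet the SAP's class list has no place for it other than a definite result.

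Evaluation of serum ADA is a secondary endpoint. The classes feed the incidence tables (14.5.1.1 and 14.5.1.2), the table by hypersensitivity reaction (14.5.1.3), and the summaries of drug concentration, Global Severity Score and time-to-BQL by antibody status (SAP 11.2.2). An uninformative negative would be counted in all of these as though it were a Day 14 negative.

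**Working it through.** **Step 1: who can have only an early sample.** Routes out of treatment or study in the first week:

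| Route | Post-dose ADA sample | Class under SAP 11.1.1 |
|---|---|---|
| Dosing never started on Day 1 | None needed (footnote u) | Not in the Safety population |
| Consent withdrawn or lost to follow-up | None | 6 or 7, inconclusive |
| Study drug stopped, infant stays in study | Day 14 visit | 1 to 5, at the planned time |
| Dosed, then withdrawn from study by the investigator for safety or for non-compliance | Day of withdrawal; no Day 28 visit | 1 to 5, by result alone |

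Only the last row is affected. If the pre-dose sample is negative and the early sample is negative, the infant goes to class 1, then to category 12 (total TE ADA negative), and to NAb class 1. If the pre-dose sample is missing, class 8 already makes the result inconclusive.

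**Step 2: does the washout reason cover these samples?** Protocol 3.4.5.1 places PK sampling between the second and third doses in order to measure serum drug. In the earlier infant study, at 1.2 mg/kg (protocol 3.3.2), drug was quantifiable in the serum of most infants (1.2.3). Target doses here are 3 to 9 mg/kg. Drug may therefore be present in a Day 2 or Day 3 sample. The assay's drug tolerance is not stated, so the conclusion is only that washout is not assured.

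**Step 3: size.** The plan states no figure for this, so the earlier study's TE ADA rate is used as an assumption.

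- Check of that rate: protocol 1.2.3 gives 3 subjects as 8.6% of the ALX-0171 group. 3/35 = 8.6% and 8/35 = 22.9%, so both percentages fit 35 treated infants.
- Let p = 8/35, and let w be the share of dosed infants whose only post-dose sample is too early and is scored negative. Reported incidence = p(1 − w).

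| w (assumed) | Reported incidence | Fall, points |
|---|---|---|
| 0% | 22.9% | 0.0 |
| 1% | 22.6% | 0.2 |
| 2% | 22.4% | 0.5 |
| 5% | 21.7% | 1.1 |
| 10% | 20.6% | 2.3 |
| 15% | 19.4% | 3.4 |

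- Per infant: 22.9/45 = 0.5 points in one arm; 22.9/135 = 0.17 points over the three active arms (3 × 45 = 135).
- Sampling error for comparison: √(0.229 × 0.771/45) = 0.063, or 6.3 points per arm.

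The 15% is the drop-out allowance in protocol 3.1.2. It covers drop-out before the primary endpoint and false-positive RSV tests, so it is a far end of the range and not an estimate of w.

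**The case against.** The strongest reply is that the SAP is silent rather than wrong. The bioanalytical laboratory does the classifying, and protocol 3.4.7.2 defers data processing to a Bioanalytical Analysis plan that is not among the documents. Protocol 3.1.2 also describes the post-dose sample as one taken 14 days after the first dose, so a laboratory could treat a Day 2 sample as not being the planned one. This stands in part: no text declares an early Withdrawal sample valid. But the SAP fixes the class list, ties inconclusive to absence, and removes on a stated ground the one class that could have held these samples. Its NAb rule for ADA-negative infants takes no account of timing.

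Four stronger readings are tempting, and the documents do not support them.

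- *Those affected are chiefly safety withdrawals.* No passage says so. Non-compliance is another route, and many safety problems end dosing only, which keeps the Day 14 sample.
- *Table 14.5.1.3 is biased toward no association.* Under protocol 3.2.3 and 3.4.8.1, a severe or serious hypersensitivity reaction stops study drug and does not itself require study withdrawal. An extra serum sample is also requested. Pre-existing antibody is measured before dosing and is untouched by withdrawal date, and the table is descriptive. A milder reaction followed by a discretionary withdrawal could still put an early negative there, and could matter if cases are few.
- *Withdrawn infants lose their safety laboratory tests and AE follow-up.* The Withdrawal visit shares a column with Day 14 and includes clinical laboratory tests. Protocol 3.5.5 has AEs followed to a stable outcome.
- *Every such infant is scored negative.* Pre-existing antibodies were found in 45% in the earlier study. Those infants may be classed TE ADA negative, positive or EQ, and the criteria are not given.

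**Conclusion.** The point holds as a gap in the classification rule. For a dosed infant withdrawn in the first week, and without pre-existing antibodies, the SAP as written turns an uninformative negative into TE ADA negative and NAb negative on treatment, and its washout reason does not cover that sample.

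The effect on overall incidence is probably small: about 0.5 points per infant in a 45-infant arm, and 3.4 points even at an assumed 15%, against a standard error of 6.3 points. These figures assume that the 22.9% rate carries over to this study's doses, that every early-sampled infant is scored negative, that such infants would have turned positive at the same rate by Day 14, and that inconclusive infants are left out of the denominator. SAP 11.1.1 does not state that denominator. The number affected is not given.

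The change is worth making because the rule is otherwise left to default, and because the small subgroup tables are more sensitive than the overall rate.

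**What to change.** In SAP 11.1.1 and 11.1.2:

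- State a minimum interval for a valid non-positive post-dose sample, for example the protocol's own 7 days from first dose, agreed with the laboratory.
- Class an infant whose last post-dose sample is earlier than that and not positive together with post-dose missing (ADA classes 6 and 7; NAb classes 5 and 6). Keep positives as positive.
- Report the number of such infants by arm, and state whether inconclusive infants enter the incidence denominator.
- Limit the washout note to Day 14 and Day 28 samples.

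Sample dates and times are already recorded (protocol 3.4.7.1), so the cost is a few sentences and a few more inconclusive infants.

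Separately, protocol 3.2.3 names safety or best interest under both study withdrawal and drug discontinuation. The second route keeps the Day 14 and Day 28 visits and the first does not. The sponsor should reconcile the two lists; this review does not say which rule should apply.

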### 11.1.2 NAb

All samples screened and confirmed positive in the ADA assay will be analyzed in the NAb assay. NAb assay results will be reported as values (ratio is optical density (OD) value over negative control (NC)). No titration will be performed.

Subjects will be classified based on their pre-dose status (i.e. baseline visit) and status on treatment as shown below. Subject classification based on NAb is performed by the external provider (Eurofins, UK) performing NAb sample analysis and they report both ratio (for all analysed samples) and NAb subject classification:

1. Pre-dose Neg – Neg on treatment
2. Pre-dose Neg – Pos on treatment
3. Pre-dose Pos – Neg on treatment
4. Pre-dose Pos – Pos on treatment
5. Pre-dose Neg – Post-dose missing
6. Pre-dose Pos – Post-dose missing
7. Pre-dose missing – Neg on treatment
8. Pre-dose missing – Pos on treatment

Subjects with no positive ADA samples, will not be analyzed in the NAb assay and will be classified as Pre-dose Neg - Neg on treatment. In listings, samples not evaluated in the NAb assay will be indicated as not analyzed (NA).

Below subject categories are only to be used in the tables and figures on incidence and subgroup analysis (for all other figures and tables subject classifications are used as described above).

Possible subject categories:

1. Pre-dose Neg – Neg on treatment
2. Pre-dose Neg – Pos on treatment
3. Pre-dose Pos – Neg on treatment
4. Pre-dose Pos – Pos on treatment
5. Pre-dose Neg – Post-dose missing
6. Pre-dose Pos – Post-dose missing
7. Pre-dose missing– Neg on treatment
8. Pre-dose missing – Pos on treatment
9. Total Pre-dose negative (“Pre-dose Neg – Neg on treatment”, “Pre-dose Neg – Pos on treatment” and “Pre-dose Neg – Post-dose missing”)

10. Total Pre-dose positive (“Pre-dose Pos – Neg on treatment”, “Pre-dose Pos – Pos on treatment” and “Pre-dose Pos – Post-dose missing”)
11. Total Neg on treatment (“Pre-dose Neg – Neg on treatment’, “Pre-dose Pos – Neg on treatment”, “Pre-dose missing-Neg on treatment”)
12. Total Pos on treatment (“Pre-dose Neg – Pos on treatment’, “Pre-dose Pos – Pos on treatment”, “Pre-dose missing-Pos on treatment”)
13. Pos on treatment within Pre-dose Neg
14. Pos on treatment within Pre-dose Pos

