### 11.2.2 Correlation of immunogenicity with PK, efficacy and safety

The drug concentrations with actual sampling times within time windows per study protocol, will be summarized over time for the subjects with extensive PK sampling, by a subset of ADA (Total Pre-Ab Neg, Total Pre-Ab Pos, Total TE ADA Neg and Total TE ADA Pos) and NAb (Total Pre-dose Neg, Total Pre-dose Pos, Total Neg on treatment and Total Pos on treatment) subject categories. Drug concentrations will also be presented graphically in mean  $\pm$  SE plots. Scatterplots displaying drug concentrations and time will be generated by ADA and NAb subject categories pre-specified above, for each treatment group.

The mean change from baseline (to Day 2, 5 hours post dose) in Global Severity Score (GSS) will be summarized by a subset of ADA (Total Pre-Ab Neg, Total Pre-Ab Pos, Total TE ADA Neg and Total TE ADA Pos) and NAb (Total Pre-dose Neg, Total Pre-dose Pos, Total Neg on treatment and Total Pos on treatment) subject categories, for each treatment group. Scatterplot displaying change from baseline in GSS score (to Day 2,5 hours post dose) will be generated by ADA and NAb subject categories pre-specified above, for each treatment group.

The viral load (time to BQL – plaque assay) will be summarized using Kaplan Meier estimates, by a subset of ADA (Total Pre-Ab Neg, Total Pre-Ab Pos, Total TE ADA Neg and Total TE ADA Pos) and NAb (Total Pre-dose Neg, Total Pre-dose Pos, Total Neg on treatment and Total Pos on treatment) subject categories, for each treatment group. Viral load (time to BQL – plaque assay) will also be presented graphically by Kaplan Meier survival curves for each ADA and NAb subject categories pre-specified above, by treatment group.

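### The NAb default rule has no completeness condition, so ADA-negative infants with a missing sample are classed negative before and on treatment, against the SAP's own missing-sample classes

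*SAP*

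**What the plan says.** SAP 11.1.2 first limits the assay: "All samples screened and confirmed positive in the ADA assay will be analyzed in the NAb assay". It then sets a default for everyone else: subjects without any positive ADA sample "will not be analyzed in the NAb assay and will be classified as Pre-dose Neg - Neg on treatment". The default has no condition on how many samples the subject gave.

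The same section lists eight NAb classes. Four are for a missing sample, among them class 5, "Pre-dose Neg – Post-dose missing", and class 7, "Pre-dose missing – Neg on treatment". No order of priority between the default and these classes is given.

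SAP 11.1.1 handles the same infants differently for ADA. Class 6 is "TE ADA inconclusive: Pre-Ab NEG – Post-dose missing" and class 8 is "TE ADA inconclusive: Pre-dose missing – Post-dose NEG". Both are left out of the total of treatment-emergent ADA negatives (category 12).

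SAP 11.2.2 summarizes drug concentration, change in GSS and time-to-BQL by NAb groups that include "Total Neg on treatment and Total Pos on treatment", as well as the two pre-dose totals.

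**The concern.** Counting an ADA-negative sample as NAb negative without running the assay is reasonable. Counting a sample that was never taken as negative is not. Because the default looks only for the absence of a positive ADA result, it cannot tell a negative sample from a missing one.

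Two things follow. One infant can be inconclusive in the ADA table and negative on treatment in the NAb table. And the NAb groups used for the PK, GSS and viral-load summaries contain infants whose status at the relevant time is unknown.

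Missing samples are foreseeable. In Protocol 3.4.9 and Table 2, immunogenicity comes second to the clinical laboratory for blood. For infants under 5 kg the sample is not drawn at screening or Day 14 if the local laboratory needs more than 2.5 mL, and it is replaced only where possible. Protocol 3.6.6 commits to reporting NAb incidence and to examining its relation with safety, PK and efficacy, so the classes will be used.

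**Working it through.** The plan states no NAb incidence and no expected share of missing samples, so there is no figure to reproduce. The check is logical first, then illustrative.

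**Step 1: every state with a missing sample.** Each sample is missing, ADA negative, ADA positive/NAb negative, or ADA positive/NAb positive. Seven combinations include a missing sample:

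| Pre-dose | Post-dose | Default read literally | Class list | Agree? |
|---|---|---|---|---|
| ADA neg | missing | class 1 | class 5 | no |
| missing | ADA neg | class 1 | class 7 | no |
| missing | missing | class 1 | none | no |
| ADA pos, NAb neg | missing | class 5 | class 5 | yes |
| ADA pos, NAb pos | missing | class 6 | class 6 | yes |
| missing | ADA pos, NAb neg | class 7 | class 7 | yes |
| missing | ADA pos, NAb pos | class 8 | class 8 | yes |

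Three of seven conflict. The other four work as intended, so no missing class is emptied altogether.

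**Step 2: effect on the totals in SAP 11.1.2.**

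- Pre-dose negative, post-dose missing: wrongly enters category 11 (total negative on treatment). Category 9 (total pre-dose negative) is unchanged, because it already includes class 5.
- Pre-dose missing, post-dose negative: wrongly enters category 9. Category 11 is unchanged, because it already includes class 7.
- Both missing: wrongly enters both.

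**Step 3: effect on incidence.** Let N be the subjects counted under the literal rule, k those wrongly placed and x the positives. The literal rule gives x/N; leaving the missing out gives x/(N − k).

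Inputs: N = 45 per arm (Protocol synopsis, number of subjects), or 3 × 45 = 135 active. Assumed, because the documents do not give them: k is 5 to 20% of N, and the NAb rate among evaluable infants is 5 to 22.9%. The upper value borrows the treatment-emergent ADA rate of the first infant study (Protocol 1.2.3) purely as an illustration. Counts are rounded to whole infants.

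For positives over positives plus negatives on treatment, with k pre-dose negative/post-dose missing:

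- N = 45, k = 2, x = 2: 2/43 = 4.7% against 2/45 = 4.4%; gap 0.2 points before rounding.
- N = 45, k = 4, x = 4: 4/41 = 9.8% against 4/45 = 8.9%; gap 0.9.
- N = 45, k = 9, x = 8: 8/36 = 22.2% against 8/45 = 17.8%; gap 4.4.
- N = 135, k = 27, x = 25: 25/108 = 23.1% against 25/135 = 18.5%; gap 4.6.

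For positives within the pre-dose negative stratum (category 13), the infants that matter are those with a missing pre-dose sample. If the literal stratum counts 45, of whom 4 had no pre-dose sample, and 5 are positive, then 5/41 = 12.2% becomes 5/45 = 11.1%.

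**Step 4: which denominator applies.** SAP 5.4.1 takes missing observations out of percentage denominators but does not say whether NAb classes 5 to 8 count as missing. Table 14.5.1.2 names the safety population. If all of that population is the denominator, x/N is reported either way and the positive percentage does not move.

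**The case against.** The author may have meant only infants with two ADA-negative samples. The sentence can be read as explaining how untested negative samples count, beside a list that provides for missing ones. An external provider does the classification, and Protocol 3.4.7.2 refers to a separate bioanalytical plan that is not available here. This is plausible, but the SAP text does not say it, and a provider working from that text would misclassify.

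Fallbacks also reduce the number affected. A missed screening sample should be taken before the first dose, and a missed Day 14 sample at Day 28, as far as possible (Protocol 3.4.7.1). The schedule also places the draw at the withdrawal visit. This stands: a post-dose result is usually missing only if the fallback fails too.

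The outputs by NAb status are descriptive, with no test specified, and the concentration summaries cover only subjects with extensive PK sampling. This also stands and limits the importance.

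A reader might infer more: that every infant with a missing sample is called negative, that NAb incidence is diluted whatever the denominator, or that the ADA secondary endpoint is affected. The documents support none of these. Infants with an ADA-positive sample still reach classes 5 to 8; dilution depends on an unstated denominator; and the ADA classification keeps these infants as inconclusive. A reader might also combine the 45% with pre-existing antibodies in the first infant study with assumed missing rates to obtain one relative bias. That would rest on missing rates and a denominator the SAP does not give.

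**Conclusion.** The point holds as a contained inconsistency. Followed as written, the default misplaces three kinds of ADA-negative infant: post-dose missing, pre-dose missing, and both missing. The first two conflict with NAb classes 5 and 7 and with ADA classes 6 and 8; the third has no class in either list. The category counts are then wrong under any denominator, and so are the NAb groups in the descriptive summaries.

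Understatement of NAb incidence is conditional. It arises if missing classes are left out of the denominator, as SAP 5.4.1 suggests, or in a within-stratum rate. It is nil with a whole-safety-population denominator. The illustrated 0.2 to 4.6 points for the on-treatment rate rest wholly on the assumed missing and NAb rates and are not an estimate for this trial. The primary endpoint analysis and the ADA classification are untouched. This is a minor correction, worth making because it is cheap.

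**What to change.** Replace the default in SAP 11.1.2 with text to this effect:

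> Class 1 applies by default only when a subject has both a pre-dose and a post-dose ADA result and neither is positive. When the available result is ADA negative, class 5 applies if the post-dose sample is missing and class 7 if the pre-dose sample is missing. A subject with neither sample is not evaluable.

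Add the not-evaluable class to the list. Exclude classes 5 and 6 and not-evaluable subjects from on-treatment denominators, since none of them has a post-dose result. State the NAb incidence denominator in SAP 11.2 and in a footnote to Table 14.5.1.2.

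The cost is a few lines in the SAP and the same wording in the instruction to the external provider. No new data or samples are needed.
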